# 9.4 FERTILITY AND CONTRACEPTION REQUIREMENTS

Females must be of nonchildbearing potential, defined as;

- 1. Surgically sterile for at least 180 days before study initiation.
- 2. Postmenopausal for at least 1 year before study initiation. Subjects claiming postmenopausal status will have a Follicle Stimulating Hormone (FSH) test performed at screening to confirm postmenopausal status.

-OR-

Females of childbearing potential must agree to use an allowable form of birth control from screening until 90 days after end-of-study. The following are allowed birth control methods:

- 1. Implanted or intrauterine hormonal contraceptive use for at least 180 continuous days before drug administration.
- 2. Oral, path, or injected contraceptives, or vaginal hormonal device in use for at least 90 continuous days before drug administration.
- 3. Intrauterine device.
- 4. Vasectomized partner (at least 90 days before drug administration).
- 5. Nonsurgical permanent sterilization (at least 90 days before drug administration).
- 6. Double barrier method (for example, diaphragm with spermicide, condoms with spermicide).

7. Abstinence (and agreement to use double barrier method if they become sexually active during the above time).

Male Subjects must agree to one of the following birth control methods from screening to 90 days after end-of-study.

- 1. Be surgically sterile for at least 90 days before screening.
- 2. Agree to use a condom with spermicide when sexually active with a female partner who is not using an acceptable method of birth control.
- 3. Abstinence (with agreement to use a condom with spermicide if they become sexually active during the study).

# 9.5 PROHIBITIONS AND RESTRICTIONS

Potential Subjects must be willing to adhere to the following prohibitions and restrictions during the study to be eligible for participation.

- 1. Subjects must remain at the study center until 24 hours after drug administration (SAD) or 24 hours after completion of the final drug administration (MAD).
- 2. Subjects must continue using an appropriate method of birth control (see section 9.4 Contraception Requirements).
- 3. Subjects must avoid excess daily consumption of methylxanthine-containing products (eg chocolate, coffee, caffeinated teas or colas) during the confinement period of the study. Excess consumption is defined as >1 serving of chocolate (1.55 ounces), 3 or more cups (0.7 liters) of coffee or caffeinated teas or colas.
- 4. Subjects must consume standard institutional meals during the confinement period of the study. Excessive food consumption is not permitted.
- 5. Subjects are not permitted to use tobacco or nicotine containing products including (but not limited to) cigarettes, e-cigarettes, cigars, bidis, kreteks, pipes, chewing tobacco, snuff, and dip during the confinement period of the study.
- 6. Subjects are not permitted to use drugs of abuse including (but not limited to) alcohol, cannabinoids, opiates, cocaine, amphetamines, benzodiazepines, hallucinogens or barbiturates during the confinement period of the study.
- 7. Subjects are not permitted to perform strenuous activity or exercise during the confinement period of the study and for 48 hours after completion of the final drug administration.
- 8. Subjects must be advised not to donate blood for at least 90 days after completion of the study or to participate in any investigational drug study for at least 90 days after completion of the study.

# 10.0 STUDY WITHDRAWAL, COMPLETION, ESCALATION, AND STOPPING CRITERIA

#### **10.1 WITHDRAWAL**

A Subject will be withdrawn from the study for any of the following reasons.

- 1. Withdrawal of consent.
- 2. Noncompliance with any of the study requirements including failure to meet eligibility criteria or violation of any of the listed prohibitions and/or restrictions.
- 3. Discontinuation of study treatment for any reason.
- 4. Subject is lost to follow-up.

Study drug assigned to the withdrawn Subject may not be assigned to another Subject and must be disposed of according to the instructions (see Drug Product Accountability).

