#### Table 1: SAD schedule of assessments and procedures

An early termination visit will be scheduled on an ad hoc basis for any subject who withdraws from the study. \* Physical examinations can be conducted at any additional time at the judgement of the Principal Investigator (eg, to evaluate an adverse event)

^FSH for postmenopausal women at screening visit

\*\* Day 1 Timepoints: 1-hr preinfusion, and 1, 2, 4, 8, and 12 hr after the start of the infusion.

\*\*\* Ocular examinations include visual acuity and color vision tests.

\*\*\*\* On Day 1, MOAA/S is performed preinfusion, during the infusion at approximately 20 min after start of infusion, 40 min after start of infusion, and approximately 1 hr after the start of the infusion.

\*\*\*\*\* On Day 1, CADSS is performed preinfusion and approximately 40 min and 80 min after the start of the infusion.

Procedure	Screening					Confin	ement					Follo	ow-Up
	(Day -28 to Day -2)	Day -1	Day 1	Day 2	Day 4	Day 5	Day 7	Day 8	Day 9	Day 11	Day 12	Day 15	Day 17-19
Informed Consent	X												
Eligibility Criteria	X	X											
Demographics	X												
Height	X												
Weight, BMI	X	X									Х		
Medical history	X	X									Χ	X	X
Physical Examination*	X	X					Χ				Χ		
Vital Signs**	X	X	Х		X	X	X	X	X	X	X		
ECG**	X	X	Х		X	X	X	X	X	X	X		
Urine Drug Test	X	X					X						
Alcohol Breath Test	X	X					X						
Pregnancy Test	X	X					X						
(Females)^													
Serology (Hepatitis C,	X												
Hepatitis B, HIV)													
Clinical Lab. Tests	Х		Х	Х				Х	Х	Х	Х		
(Hema., Chem.,													
Urinalysis)													
Prior and Concom. Meds.	X	X	X			X	X				X	X	X
Ocular Examinations***		X		X						X	X		
Modified Observer's			Х		Х			Х		Х			
Assess. of Alert./Sed.													
(MOAA/S)****													
Suicide Screening (C- SSRS)	X	X	X	X	X	X	X	X	X	X	X	X	X
Mood and Cognitive		X	X	X	X	X	X	X	X	X	X	X	X
Assessment (POMS)													
Clin. Admin. Diss. States			X		X			X		X			
Scale (CADSS)*****													
IV Drug Administration			X		X			X		X			
Blood Sample Coll. (PK)			X	X	X			X		X	X		
Check-in & Confinement		X	X	X	X		X	X	X	X			
Check-out*****						X					X		
Adverse Events			X	X	X	X		X	X	X	X	X	X
Outpatient Visit													
Phone Call												X	Х

Table 2: MAD schedule of assessments and procedures

An early termination visit will be scheduled on an ad hoc basis for any subject who withdraws from the study.

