#### **10.2 REPLACEMENT**

Subjects who withdraw before receiving the study drug will be replaced. Following dosing, 1 subject per cohort may withdraw before completion and may or may not be replaced, at the discretion of the Investigator. Should more than 1 subject from the same cohort voluntarily withdraw from the study following dosing, those subjects will be replaced unless withdrawal was due to a safety or tolerability issue. Subjects who received any amount of the study drug and who withdraw or are withdrawn from the study will be encouraged to continue follow-up (with subjects' consent) for safety. Subjects withdrawing will be asked to complete an early termination visit if they do not wish to be followed per protocol. Any decision to replace a subject who drops out after receiving the study drug will be documented in the electronic data capture (EDC) system on an electronic case report form (CRF).

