#### Individual Halting Rules

The following individual halting rules pertain to the MAD study only:

- Any SAE.
- Any other condition that the site PI judges to unduly increase the risk to the subject.

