Abuse-related AEs will be reported separately and include a case narrative. Case narratives will include the time of onset and duration of the event, dose of drug taken, severity, and outcomes. A pharmacokinetic analysis will also be performed to assess if an abuse-related AE correlates with drug exposure.

The relationship between the AE and investigational product (IP) will be determined by the PI based on his or her clinical judgement and the following definitions.

**Related**: The AE follows a reasonable temporal sequence from the study product administration and cannot be reasonably explained by the Subject's clinical state or other

factors. The AE follows a reasonable temporal sequence from the study product administration and represents a known reaction to the drug under study or other drugs in its class or is predicted by the known pharmacological properties of the drug.

**Not Related**: The AE does not follow a reasonable temporal sequence from study product administration or can be reasonably explained by the Subject's clinical state or other factors.

**Pregnancies**: Pregnancies will be documented and followed until birth or another outcome. Pregnancies will not be reported as AEs. However, if at any time the pregnancy outcome falls under the scope and definition of a SAE, it will be reported as such.

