12.1 Subject Disposition

Analysis populations will be summarized by study (SAD/MAD/CSF), cohort, and treatment assignment. The Safety Population will be used for any additional Subject Disposition analyses.

The number and percentage of subjects who completed and prematurely discontinued the study will be presented by study drug and overall vs placebo for the Randomized Population. Reasons for premature discontinuation as recorded on the completion page of the CRF will be summarized, as applicable.

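### Protocol 10.1 treats stopping study drug as leaving the study, so the remaining scheduled safety assessments become voluntary and the remaining PK samples are not provided for

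*Protocol*

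**What the plan says.** Section 10.1 of the protocol opens its list with "A Subject will be withdrawn from the study for any of the following reasons". Item 3 of that list is "Discontinuation of study treatment for any reason". Item 2 covers noncompliance with any study requirement.

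Section 10.2 deals with what follows: "Subjects who received any amount of the study drug and who withdraw or are withdrawn from the study will be encouraged to continue follow-up", with consent and for safety. It adds: "Subjects withdrawing will be asked to complete an early termination visit if they do not wish to be followed per protocol". The schedules of assessments for all three parts describe that visit in one line: "An early termination visit will be scheduled on an ad hoc basis for any subject who withdraws from the study". They give no content, timing or PK sample for it.

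Other passages bear on the same subjects:

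- Section 10.3, individual halting rules (MAD only): any SAE, or "Any other condition that the site PI judges to unduly increase the risk to the subject".
- Section 12.9: SAEs are followed to satisfactory resolution and all AEs to resolution when possible. An AE or SAE triggers sensory and motor examination, vital signs, optional extra blood or CSF, and a Day 30 call. For abuse-related events, "A pharmacokinetic analysis will also be performed to assess if an abuse-related AE correlates with drug exposure".
- Section 12.4: a positive alcohol, cotinine or drug test at any time ends participation.
- SAP 6.2 keeps every dosed subject in the Safety Population. SAP 7 uses the available data without imputation.
- SAP 12.1: "The number and percentage of subjects who completed and prematurely discontinued the study will be presented", with reasons.

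**The concern.** The two primary objectives are the safe dose range and the pharmacokinetics. Subjects taken off drug because of an event are directly informative on both: what their exposure was, and how they recovered. Under 10.1 the event that stops the drug also ends required participation, so whether later data exist depends partly on the outcome being studied.

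Three uses of the data are affected. By-visit safety summaries rest on whoever has values. The MAD escalation review in section 10.3 looks at the available safety data to Day 12 at a minimum. The exposure analysis of abuse-related events in 12.9 needs concentrations from subjects who may have been stopped for such an event. With 6 active subjects per SAD or MAD cohort, each is 1/6, or 17%, of the active group.

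**Working it through.** This is mainly a reading of text, followed by counts from the schedules.

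**1. What the rule does.** 10.1 makes study withdrawal mandatory once treatment is discontinued. No passage defines a subject who is off treatment but still in the study. A MAD subject halted under 10.3 therefore falls under item 3 and then depends on 10.2.

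**2. What remains required afterwards.** The AE-triggered list in 12.9 contains neurological tests, vital signs and a Day 30 call. Set against the schedules, it leaves out ECG, clinical laboratory tests, ocular examinations, POMS, CADSS and C-SSRS. Scheduled PK is also absent; extra blood or CSF is at the investigator's discretion. These scheduled items are the part that becomes voluntary or is left unaddressed.

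**3. MAD, PK count.** The plan states 20 timepoints (protocol 8.6). By dose this is 8 + 2 + 2 + 8 = 20, so the figure reproduces. If an infusion were stopped partway with only the preinfusion sample taken, the samples still due for that dose would be:

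- dose 1 or dose 4: 8 − 1 = 7 of 8
- dose 2 or dose 3: 2 − 1 = 1 of 2

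After a completed dose 2, the only PK sample due before dose 3 is the Day 8 predose sample.

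**4. MAD, safety count (Table 2).** C-SSRS and POMS are scheduled after first dosing on Days 1, 2, 4, 5, 7, 8, 9, 11, 12, 15 and 17-19, which is 11 occasions. A subject stopped after the Day 4 dose has 8 of these ahead. Days 8, 9, 11 and 12 are dosing days, or the day after, for doses 3 and 4, which this subject does not receive. That leaves 8 − 4 = 4 occasions (Days 5, 7, 15, 17-19) not tied to a dose not given. All later laboratory tests (Days 8, 9, 11, 12), ocular examinations (Days 11, 12) and CADSS (Days 8, 11) fall on the other four days. Those are nevertheless the only scheduled laboratory and ocular checks left after stopping.

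**5. SAD and CSF.** There is one infusion, so item 3 can apply only if it is interrupted. SAD has 9 blood timepoints, of which 9 − 1 = 8 come after the preinfusion sample. If sampling ended (an assumption), up to 8 of 9 would be lost and neither AUC nor half-life could be estimated for that subject; section 13.2 calculates parameters only where the collected samples allow. In the CSF part the same count is 7 of 8 blood samples and 2 of 3 CSF samples.

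**6. How often it could matter.** No discontinuation rate is given, so a range is assumed. P(at least one) = 1 − (1 − p)^n, with subjects independent:

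| Assumed rate p | 6 active (one cohort) | 12 active (all MAD) |
|---|---|---|
| 5% | 26.5% | 46.0% |
| 10% | 46.9% | 71.8% |
| 20% | 73.8% | 93.1% |

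To illustrate the cost of a lost subject, suppose a late finding visible only on scheduled tests has a true rate of 20%. The chance of seeing it at least once is 1 − 0.8^6 = 73.8% with 6 followed, 1 − 0.8^5 = 67.2% with 5, and 1 − 0.8^4 = 59.0% with 4.

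**The case against.** A reader might infer several stronger conclusions. The documents do not support them.

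- *PK sampling ends at discontinuation.* No passage says so. 10.2 leaves open that a withdrawn subject is followed per protocol, which could include the remaining samples, and 12.9 allows extra blood after an AE. The PK Analysis Plan and the Manual of Procedures are not part of the documents. The text is silent rather than prohibitive.
- *Safety follow-up becomes optional altogether.* 12.9 requires AE and SAE follow-up, set measurements and a Day 30 call, and does not limit them to subjects still in the study. An SAE also stops the whole study under 10.3.
- *These subjects drop out of the analysis.* SAP 6.2 keeps them. What can be missing is later data.
- *The SAP cannot tell stopping drug from leaving the study.* SAP 6.5 defines a population that completed all doses, SAP 12.1 summarises the populations and the reasons for discontinuation, and SAP 12.3 gives exposure with individual listings. Incomplete dosing is therefore visible. What is lacking is a tabulation of treatment discontinuation as its own status.

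It is also fair to say that later MAD visits describe mainly those who tolerated the drug under any rule, since halted subjects get no further doses. Keeping them would mix off-drug values into the Day 8 to Day 12 summaries unless these are marked. And in the example of a subject stopped after a complete dose 2, almost no PK is at stake.

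These points narrow the concern but leave its core: the withdrawal is mandatory, the scheduled assessments are only encouraged, the remaining PK samples are not mentioned, and the early termination visit is empty.

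**Conclusion.** The point holds in a limited form. 10.1 merges treatment discontinuation with study withdrawal, and 10.2 does not undo this for the scheduled assessments or for PK. The practical reach is the 12 active MAD subjects, plus any SAD or CSF subject whose infusion is interrupted.

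The size depends on assumptions. The 8 of 9 SAD samples is an upper bound, conditional on sampling stopping. The 8 of 11 MAD occasions is a correct count, but half of them belong to doses not given. The probabilities in the table rest on assumed rates. Within those limits, the rule allows outcome-dependent missing data on both primary objectives, and this can be avoided cheaply. It should be changed, but it does not invalidate the design.

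**What to change.** In the protocol:

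- In 10.1, separate study treatment discontinued from withdrawn from study, so that treatment discontinuation alone does not end participation.
- State that, with consent, the remaining scheduled safety assessments and the remaining PK samples of the last dose received continue, and that the dose actually given and the stop time are recorded.
- List the content of the early termination visit.
- Reconcile 10.1 and 10.2 with the follow-up duties in 12.9, and with 12.4 on ending participation after a positive test. MAD subjects repeat drug and alcohol tests on Day 7, after two doses, so already dosed subjects can be affected.

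In the SAP:

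- In 12.1, tabulate treatment discontinuation and study discontinuation separately, each with reasons.
- Mark off-treatment values in the MAD by-visit summaries, so that they are not read as on-drug results.

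The cost is wording in both documents and procedures already in the schedule, with a small extra burden on the few subjects who stop. The rules on when to stop treatment are left as they are.

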#### **10.2 REPLACEMENT**

Subjects who withdraw before receiving the study drug will be replaced. Following dosing, 1 subject per cohort may withdraw before completion and may or may not be replaced, at the discretion of the Investigator. Should more than 1 subject from the same cohort voluntarily withdraw from the study following dosing, those subjects will be replaced unless withdrawal was due to a safety or tolerability issue. Subjects who received any amount of the study drug and who withdraw or are withdrawn from the study will be encouraged to continue follow-up (with subjects' consent) for safety. Subjects withdrawing will be asked to complete an early termination visit if they do not wish to be followed per protocol. Any decision to replace a subject who drops out after receiving the study drug will be documented in the electronic data capture (EDC) system on an electronic case report form (CRF).

#### **10.3 ESCALATION, CONTINUATION, AND STOPPING RULES**

Criteria surrounding sentinel halting, study halting and/or dose escalation within the SAD portion of the study and study halting and/or dose continuation within the MAD portion of the study will governed by the following criteria.

#### Study Halting Rules

If any of the following events occur, the study will be stopped:

- Any subject develops an SAE through the last study visit.
- 2 or more subjects in any cohort experience a Grade 3 (severe) AE, including unsolicited clinical, ECG, VS, and laboratory AEs, that is of the same type (preferred term) and occurring in the same SOC.
- Any subject develops an episode of anaphylaxis within 24 hours after receiving the study drug.

#### Dose Escalation Halting Rules

The PI must review the following criteria before dose escalation:

- SAD: A review of all available safety data for the cohort to Day 3 demonstrates that the study halting criteria described below have not been met.
- MAD: A review of all available safety data to Day 12, at a minimum, demonstrates that the dose-escalation halting criteria described below have not been met.

If any of the following dose escalation halting rules are met in either the SAD or MAD parts, escalation to the next planned dose cohort will not proceed until all available study data have been reviewed by the PI, the Medical Monitor and the Study Sponsor:

- Any subject develops an SAE.
- Any subject experiences a Grade 3 (severe) AE.
- 2 or more subjects in a cohort experience a Grade 2 (moderate) or greater AE that is of the same type (preferred term) and occurring in the same SOC.

#### Individual Halting Rules

The following individual halting rules pertain to the MAD study only:

- Any SAE.
- Any other condition that the site PI judges to unduly increase the risk to the subject.

## Sentinel Halting Rules

The following are SAD sentinel halting criteria, ie, if any are met, the rest of the cohort will not be dosed until reviewed by the PI, the Medical Monitor and the Study Sponsor:

• Any subject develops a Grade 3 (severe) AE within 24 hours of study drug administration.

If stopping rules are triggered for any reason, the study PI will notify the Medical Monitor and the Study Sponsor and initiate a review that may include unblinding of treatment assignments. A summary of the decision making for all halts will be documented and submitted to the IRB.

In the event that any of the stopping criteria are triggered, the PI in consultation with the Medical Monitor and Study Sponsor may take one of the following courses of action.

- 1. Temporarily halt dosing while the event is investigated.
- 2. Declare the prior tested dose level as the MTD.
- 3. Recommend repeat dosing at the same level.
- 4. Recommend dosing at an intermediate level.
- 5. Recommend protocol amendment to increase Subject safety.
- 6. Discontinue the study.

# **11.0 STUDY DRUG INFORMATION**

#### 11.1 DRUG PRODUCT IDENTITY, MANUFACTURE, SHIPMENT, AND RECEIVING

The Clinical Trial Materials include the IDP, buffered vehicle, and placebo. The IDP is a solution-based formulation of (2R,6R)-Hydroxynorketamine Hydrochloride. The diluting vehicle is a 25 mM sodium phosphate (pH 7) buffer in 0.9% (normal) saline solution. The placebo is 0.9% (normal) saline. The IDP will be manufactured by a Good Manufacturing Practice (GMP) certified contract manufacturing organization (CMO) as a 10 mg/mL (free base equivalent) sterile solution using a 25 mM sodium phosphate (pH 7) buffer in 0.9% (normal) saline. The buffered vehicle is sterile solution using a 25 mM sodium phosphate (pH 7) buffer in 0.9% (normal) saline. The buffered vehicle is sterile solution using a 25 mM sodium phosphate (pH 7) buffer in 0.9% (normal) saline and will be manufactured by a GMP certified CMO. Placebo will be sourced by the Duke Clinical Research Institute (DCRI).

The IDP will be manufactured, shipped, and stored in individual 100 mL (total volume) Type I clear glass vials containing a total volume of 55 mL of IDP. The IDP will be labeled according to FDA regulatory requirements.

The buffered vehicle will be manufactured, shipped, and stored in individual 100 mL (total volume) Type I sterile glass vials. The buffered vehicle will be labeled according to FDA regulatory requirements.

